5.2.2.3 Temporary Study Drug Interruptions

Treatment with study drug should be temporarily stopped for up to 7 days under the following conditions:

1. In case of oral surgery (including dental extraction), oral injury or other oral conditions affecting the integrity of the oral mucosa to allow healing of the oral cavity (not including loss of deciduous teeth);
2. Other reasons as deemed necessary by the investigator or designee.

If a subject has a treatment interruption due to a worsening AE related to the study drug, then the subject should be re-evaluated by the investigator, or designee, prior to reinitiating the study drug.

5.2.3 Trial Blinding/Masking

A double-blind/masking technique will be used. MK-3641 and placebo will be packaged identically so that blind/masking is maintained. The subject/parent/guardian, the investigator and Sponsor personnel or delegate(s) who are involved in the treatment administration or clinical evaluation of the subjects are unaware of the group assignments.

See Section 7.1.4.2, Blinding/Unblinding, for a description of the method of unblinding a subject during the trial, should such action be warranted.

5.3 Randomization or Treatment Allocation

Randomization will occur centrally using an interactive voice response system / integrated web response system (IVRS/IWRS). There are 2 treatment arms. Subjects will be assigned randomly in a 1:1 ratio to MK-3641 and placebo, respectively.

5.4 Stratification

Randomization will be stratified according to the following factors:

1. Age (5 to 11 years, 12 to 17 years);
2. Asthma status (asthma, non-asthma) of the subjects.

5.5 Concomitant Medications/Vaccinations (Allowed & Prohibited)

Medications or vaccinations specifically prohibited in the exclusion criteria are not allowed during the ongoing trial. If there is a clinical indication for any medication or vaccination specifically prohibited during the trial, discontinuation from trial therapy or vaccination may be required. The investigator should discuss any questions regarding this with the Sponsor Clinical Director. The final decision on any supportive therapy or vaccination rests with the investigator and/or the subject's primary physician. However, the decision to continue the subject on trial therapy or vaccination schedule requires the mutual agreement of the investigator, the Sponsor and the subject.

Restrictions for concomitant therapy beginning prior to the start of the ragweed season (with the listed washout requirements) and continuing for the duration of the study (with the exception of study-provided rescue medications) are listed in [Table 5](#). Those medications listed in [Table 3](#) are prohibited beginning with the washout periods prior to randomization and continuing for the duration of the study.

Table 5 Prohibited Medications Beginning Prior to Pre-Season Visit 6 and for Duration of Trial

Prohibited Medication(s)	Washout Period Prior to Pre-Season Visit 6
Long-acting parenteral (intramuscular, intra-articular) corticosteroids	90 days
Oral corticosteroids	60 days
Nasal corticosteroids	30 days
Short-acting parenteral corticosteroids	30 days
Leukotriene antagonists/synthase inhibitors	30 days
Corticosteroid eye drops	30 days
Inhaled, topical, or oral nedocromil or cromolyn sodium	14 days
Oral or topical antihistamines ^a	7 days
Nasal or ocular decongestants	7 days

^a Pre-treatment with medications (e.g., antihistamines) to treat potential AEs will not be permitted; this is to avoid masking or delayed reactions.

Medications or vaccines that are not restricted by the protocol ([Table 3](#) and [Table 5](#)) and that would not be expected to interfere with the conduct of the study are allowed. Chronic medications should be dosed on a stable regimen. All concomitant medications must be appropriately documented on the electronic case report form (eCRF). The use of any concomitant medication must relate to the documented medical history, prophylaxis, or an AE of the subject.

5.6 Rescue Medications & Supportive Care

5.6.1 Allergy Rescue Medications for Rhinoconjunctivitis Symptoms

Subjects may experience allergy symptoms that require additional treatment. Thus, rescue medications for rhinitis/conjunctivitis symptoms will be provided (beginning at Visit 6) according to the following steps (for dosage instructions, see [Table 2](#); for subject instructions, see Section 12.6):

1. Step 1: Loratadine syrup, 1 mg/mL or loratadine oral tablet, 5 mg (5 years old) or 10 mg (≥ 6 years old)
2. Step 1b: Olopatadine hydrochloride ophthalmic solution, 0.1%
3. Step 2: Mometasone furoate monohydrate nasal spray, 50 mcg.

5.6.2 Medications for Asthma Symptoms

Short-acting inhaled beta₂-agonist (i.e., albuterol/salbutamol metered-dose inhaler) will be provided to those subjects with asthma. Other medications for asthma will not be provided. Subjects who are taking low or medium daily dose inhaled corticosteroids for asthma management will be allowed to continue with the same medications during the study. A subject must have been using a low or medium daily dose of ICS for at least 12 weeks before screening and/or randomization and must have been on a stable regimen (daily dose unchanged) for at least 2 weeks before Screening (Visit 1) and/or 4 weeks before Randomization (Visit 2). Low and medium daily doses of inhaled corticosteroids are defined in [Table 1](#) (Section 4.2.1).

If a subject requires additional asthma medications, the subject should follow recommendations regarding medication adjustments provided by his/her physician. Medication use should be recorded on the eCRF.

5.6.3 Rescue Medication for Severe Allergic Reactions (Self-Injectable Epinephrine)

Self-injectable epinephrine will be provided to each subject/parent/guardian at the randomization visit (Visit 2) in countries where it is a regulatory requirement, and should be available around the time that the tablets are administered at home.

Self-injectable epinephrine is intended for immediate self-administration for an anaphylactic reaction, including symptoms/signs of upper airway obstruction. Anaphylaxis is likely when multiple organ systems are adversely affected following exposure to an allergen. A list of symptoms that may be present during anaphylaxis include flushing, apprehension, syncope, tachycardia, thread or unobtainable pulse associated with a fall in blood pressure, vomiting, diarrhea and abdominal cramps, wheezing, dyspnea due to laryngeal spasm, lower airway obstruction, pruritus, rashes (such as urticaria), or angioedema. Self-injectable epinephrine should be administered promptly (in countries where it is part of usual care) when significant respiratory and/or cardiovascular symptoms accompany an allergic reaction.

If eligible for enrollment after completing all of the screening procedures, the subject/parent/guardian in countries where epinephrine is a regulatory requirement will be provided with self-injectable epinephrine at the Randomization Visit (Visit 2). The investigator or designee will instruct the subject/parent/guardian on how to administer the self-injectable epinephrine and have it available when tablet(s) are administered. The investigator or designee will provide and explain to the subject/parent/guardian written instructions, and will review when to administer the self-injectable epinephrine. The investigator/designee will complete an Anaphylaxis Emergency Action Plan⁷ for each

⁷ The Anaphylaxis Emergency Action Plan can be modified outside the US to meet local standards for the use (or type) of epinephrine dispensed, and for calls to 911 or alternative local emergency services.

subject, provide a copy to the subject/parent/guardian, and keep a copy for the site's records (Section 12.8).

In the event that self-injectable epinephrine is used, the subject/parent/guardian must immediately call the local emergency number and the 24-hour investigational site emergency number indicated in the informed consent and on the subject identification card. An unscheduled visit will be arranged to further evaluate the subject. The investigator or designee must notify the Sponsor within 1 working day of first becoming aware of the use of self-injectable epinephrine. The symptoms and/or circumstances that triggered the use of self-injectable epinephrine must be clearly recorded on the eCRF.

5.7 Diet/Activity/Other Considerations

Subjects will be allowed to consume their usual diet and engage in their usual level of exercise throughout the trial.

5.8 Subject Withdrawal/Discontinuation Criteria

Subjects may withdraw consent at any time for any reason or be dropped from the trial at the discretion of the investigator should any untoward effect occur. In addition, a subject may be withdrawn by the investigator or the Sponsor if enrollment into the trial is inappropriate, the trial plan is violated, or for administrative and/or other safety reasons. Specific details regarding discontinuation or withdrawal procedures; including specific details regarding withdrawal from Future Biomedical Research, are provided in Section 7.1.4 – Other Procedures.

Discontinuation from treatment is “permanent”. Once a subject is discontinued, he/she shall not be allowed to restart treatment.

A subject must be discontinued from the trial for any of the following reasons:

- The subject or legal representative (such as a parent or legal guardian) withdraws consent.
- The subject experiences an SAE (not including those only associated with an overdose) which is considered treatment related, OR a causal association cannot be ruled out, OR the cause of the SAE is unknown.
- The subject experiences persistent and escalating adverse reactions in the mouth or throat.
- The subject experiences severe or persistent symptoms of esophagitis.
- The subject experiences an anaphylactic reaction with severe symptoms associated with the investigational treatment.
- The subject experiences a severe asthma exacerbation (such as requiring hospitalization or oral corticosteroid use) or the subject's asthma becomes difficult to control.
- The subject experiences other persistent, intolerable AEs considered to be due to the study treatment, as determined by the investigator or the subject/parent/guardian.

- The subject has a medical condition or personal circumstance which, in the opinion of the investigator and/or Sponsor, places the subject at unnecessary risk through continued participation in the trial or does not allow the subject to adhere to the requirements of the protocol.
- The subject is unable to tolerate the study medication, as perceived by the investigator or subject.
- The subject fails to comply with the dosing (see Sec 7.1.1.15), evaluations, or requirements of the study, despite documentation at the site of repeated efforts to reinforce compliance.
- The subject has a confirmed positive serum pregnancy test.
- The subject becomes pregnant.

5.9 **Subject Replacement Strategy**

A subject who discontinues from the trial will not be replaced.

5.10 **Beginning and End of the Trial**

The overall trial begins when the first subject signs the informed consent form. The overall trial ends when the last subject completes the last study-related phone call or visit, discontinues from the trial or is lost to follow-up (i.e. the subject is unable to be contacted by the investigator).

5.11 **Clinical Criteria for Early Trial Termination**

Early trial termination will be the result of the criteria specified below:

1. Treatment-related death of an individual;
2. Treatment-related anaphylactic shock in at least 2 subjects*.

* The criterion for 2 events is based on prior trial experience where it has been observed that events of severe anaphylactic reactions unrelated to investigational medicinal product (IMP) may occur in allergic trial subjects even with a temporal relationship to tablet administration.

Study drug intake may only be resumed after the information has been presented to health authorities, and health authorities concur with continued drug intake. In case of complete premature termination of the trial, participating investigators/subjects/parent/guardian, the IRB/ERC, and the relevant health authorities must be promptly informed of the termination.

6.0 TRIAL FLOW CHART

Trial Period:	Screening	Treatment						Post-treatment
Visit Number:	1	2	3	4/5 ^a	6	7	8	--
Visit Title:	Screening	Randomization	Off-Season	Off-Season	Pre-Season	In-Season	End-of-Season/ Discontinuation	Telephone/ Follow-up
Scheduled Day/Week:	Weeks -52 to -1 ^b	Day 1	Week 4 ^c	Midway between Visits 3 & 6	~2 weeks before start of RS	~3 weeks after start of RS ^d	~1 week after end of RS	Post 14 days
Scheduling Window (Days):	-	-	+7 days		± 7 days		± 7 days	± 5 days
Administrative Procedures								
Informed Consent ^e	X							
Informed Consent for Future Biomedical Research ^f	X							
IVRS/IWRS	X	X	X	X	X	X	X	
Inclusion/Exclusion Criteria	X	X						
Demography	X							
Medical History	X	X						
Allergic Rhinitis Baseline Profile and Family History of Atopy	X	X						
Prior/Concomitant Medication Review	X	X	X	X	X	X	X	X
Issue/Update Subject Identification Card	X	X ^g						
Issue/Instruct in the use of e-diary				X				
Review e-diary data and instructions for use					X	X		
Activate Medication section of e-diary					X			
Discontinue/Collect e-diaries							X	
Dispense/Review Anaphylaxis Emergency Action Plan ^h		X	X	X	X	X		
Provide Self-Injectable Epinephrine and Educational Information, Instruct in its use ⁱ		X						

Trial Period:	Screening	Treatment						Post-treatment
Visit Number:	1	2	3	4/5 ^a	6	7	8	--
Visit Title:	Screening	Randomization	Off-Season	Off-Season	Pre-Season	In-Season	End-of-Season/ Discontinuation	Telephone/ Follow-up
Scheduled Day/Week:	Weeks -52 to -1 ^b	Day 1	Week 4 ^c	Midway between Visits 3 & 6	~2 weeks before start of RS	~3 weeks after start of RS ^d	~1 week after end of RS	Post 14 days
Scheduling Window (Days):	-	-	+7 days		± 7 days		± 7 days	± 5 days
Provide albuterol/salbutamol to subjects with asthma ^j		X	X ^j	X ^j	X ^j	X ^j		
Issue/Instruct in the use of SLIT Report Card		X						
Collect/Review SLIT Report Card			X					
Issue/Instruct in the use of Comment Card		X	X	X	X	X		
Collect/Review Comment Card			X	X	X	X	X	
Clinical Procedures/Assessments								
Vital Signs (Temperature, Blood Pressure, Pulse, Respiration Rate) ^k	X	X	X	X	X	X	X	
Body Height and Weight ^k	X	X						
Physical Examination	X						X ^k	
Oropharyngeal Examination ^l	X	X ^l	X	X	X	X	X	
Pulmonary Function Tests ^m	X	X			X	X	X	
Beta ₂ -agonist reversibility ⁿ		X						
Skin Prick Test	X							
Adverse Events Monitoring		X	X	X	X	X	X	X
On-site Dosing of Study Medication		X						
Dispense Study Medication		X	X	X	X	X		
Verify Subject has Self-Injectable Epinephrine and Review Instructions for use			X	X	X	X		
Verify subjects with history of asthma have albuterol/salbutamol			X	X	X	X		
Check/Collect Study Medication			X	X	X	X	X	

Trial Period:	Screening	Treatment						Post-treatment
Visit Number:	1	2	3	4/5 ^a	6	7	8	--
Visit Title:	Screening	Randomization	Off-Season	Off-Season	Pre-Season	In-Season	End-of-Season/ Discontinuation	Telephone/ Follow-up
Scheduled Day/Week:	Weeks -52 to -1 ^b	Day 1	Week 4 ^c	Midway between Visits 3 & 6	~2 weeks before start of RS	~3 weeks after start of RS ^d	~1 week after end of RS	Post 14 days
Scheduling Window (Days):	-	-	+7 days		± 7 days		± 7 days	± 5 days
Dispense/Review Need for Allergy Rescue Medication					X	X		
Record Use of Allergy Rescue Medication (e-diary)					X	X	X	
Collect Rescue Medication/Self-Injectable Epinephrine							X	
Monitor compliance with Study Medication			X	X	X	X	X	
Monitor Compliance with e-dairy completion				X	X	X	X	
Laboratory Procedures/Assessments								
Serum specific IgE to a panel of allergens	X							
Hematology, Chemistry, Urinalysis	X							
Urine Pregnancy Test – if applicable ^o	X	X	X	X	X	X	X	
Immunologic sample (IgE, IgG ₄) ^p		X			X		X	
Saliva (DNA) for Future Biomedical Research ^q		X						
DNA = deoxyribonucleic acid; e-diary = electronic diary; FBR = future biomedical research; FEV ₁ = forced expiratory volume in 1 second; IgE = immunoglobulin E; IgG ₄ = immunoglobulin G ₄ ; IVRS/IWRS = Interactive Voice/Web Response System; PFT = pulmonary function test; RS = ragweed season; SLIT= sublingual immunotherapy; US = United States. ^{a.} All subjects are to complete Visit 4 midway between Visit 3 and Visit 6, but not more than 6 to 8 weeks after Visit 3. If time between Visits 4 & 6 is > 6 to 8 weeks, then subject should be scheduled to return for Visit 5 approximately midway between Visits 4 and 6; study drug is not dispensed at Visit 5 (see Section 9.2 for the visits when study drug is dispensed). ^{b.} During the first season of screening, subjects may be in screening up to approximately 9 months (-39 to -1 week). During subsequent season(s) of screening, subjects may be in screening up to approximately 12 months (-52 to -1 week). ^{c.} Visit 3 should be scheduled on Day 28 (+7 days) to allow the subject to complete the SLIT Report Card for ~28 days. ^{d.} It is preferable that Visit 7 be scheduled approximately 3 weeks after the start of the ragweed season. ^{e.} Informed consent/assent must be obtained before any trial-related procedures are performed. ^{f.} Informed consent for future biomedical research samples (optional) must be obtained before the saliva for DNA sample. ^{g.} Update Subject Identification Card with randomization number. ^{h.} The Anaphylaxis Emergency Action Plan can be modified outside the US to meet local standards for the use (or type) of epinephrine dispensed, and for calls to 911 or alternative local emergency services.								

Trial Period:	Screening	Treatment						Post-treatment
Visit Number:	1	2	3	4/5 ^a	6	7	8	--
Visit Title:	Screening	Randomization	Off-Season	Off-Season	Pre-Season	In-Season	End-of-Season/ Discontinuation	Telephone/ Follow-up
Scheduled Day/Week:	Weeks -52 to -1 ^b	Day 1	Week 4 ^c	Midway between Visits 3 & 6	~2 weeks before start of RS	~3 weeks after start of RS ^d	~1 week after end of RS	Post 14 days
Scheduling Window (Days):	-	-	+7 days		± 7 days		± 7 days	± 5 days

- ^{i.} Self-injectable epinephrine is provided only in those countries where it is a regulatory requirement.
- ^{j.} Albuterol/salbutamol should also be dispensed to subjects diagnosed with asthma during the trial as needed.
- ^{k.} Vital Signs (axillary temperature, blood pressure, pulse, respiration rate) in a seated position, height, and weight should be performed prior to performing pulmonary function tests. At the End-of-season/Discontinuation visit a limited physical exam will be performed.
- ^{l.} Oropharyngeal examinations will be performed before and after study drug administration at Visit 2. Targeted physical examinations may be conducted at visits that do not already include a physical exam, if deemed necessary by the investigator, due to signs/symptoms.
- ^{m.} FEV₁ results should be available and reviewed by investigator or designee prior to administration of first dose of study medication to ensure results meet inclusion criteria. Following randomization, PFTs are required only for subjects with asthma at the subsequent visits identified in the trial flow chart, unless the investigator feels a PFT is warranted for a subject without asthma. Note: PFTs are not required for those subjects ≤7 years of age who cannot perform reproducible FEV₁ maneuvers despite coaching; those subjects ≤7 years of age who can perform reproducible FEV₁ maneuvers, including those who initially could not at the Screening Visit, must complete the PFTs.
- ^{n.} Beta₂-agonist reversibility (Section 12.9) will be performed at Visit 2 for all subjects performing PFTs (i.e., all subjects >7 years of age and all subjects ≤7 years of age who can perform reproducible FEV₁ maneuvers).
- ^{o.} If a urine test result is positive, confirm with a serum β-hCG test.
- ^{p.} Immunologic samples will only be collected at selected sites. The Visit 2 sample should be collected prior to administration of the first dose of study drug. Leftover main study serum samples will be stored for future biomedical research if the subject consents to future biomedical research.
- ^{q.} Saliva (DNA) for FBR should be the last procedure performed at Visit 2. If not obtained at Visit 2, can be obtained at a subsequent visit once the informed consent for FBR is obtained.

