7.1.2.2 Body Height and Weight

The subject's body height and weight will be recorded as noted on the Trial Flow Chart (Section 6.0).

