7.1.2.5 Pulmonary Function Tests

Pulmonary function tests (PFTs) will include measurements of FEV₁, FEV₁ percent predicted, forced vital capacity (FVC), and FVC percent predicted for all subjects at Visits 1 and 2 (exception: those subjects ≤ 7 years of age who cannot perform reproducible PFT maneuvers despite coaching). PFTs will continue to be performed as noted on the Trial Flow Chart (Section 6.0) for those subjects with asthma (exception: those subjects ≤ 7 years of age who cannot perform reproducible PFT maneuvers despite coaching). For those subjects ≤ 7 years of age who could not perform reproducible PFT maneuvers at Visit 1, it is expected that sites will try to obtain reproducible PFT maneuvers at subsequent visits (Visit 2 for all subjects and subsequent visits for those with asthma). PFTs may also be performed at a

subsequent visit for those subjects without asthma at baseline if the investigator or designee considers a PFT is warranted.

Beta2-agonist reversibility (Section 12.9) will be performed at Visit 2 for all subjects performing PFTs (i.e., all subjects >7 years of age and all subjects ≤7 years of age who can perform reproducible FEV1 maneuvers); beta2-agonist reversibility is not an entry criterion for this study.

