- Change from baseline in vital sign parameters at each post-baseline visit;
- Change from baseline in pulmonary function test parameters at each post-baseline visit;
- Summaries by SOC for general AEs, serious AEs, drug-related AEs, serious and drug-related AEs, and AEs resulting in discontinuation;
- Average duration of AEs in minutes on Day 1;
- Average duration of AEs in days over Day 2 to Day 14;
- Average duration of AEs in days over Day 15 to Day 28.

Point estimates will be provided for the Tier 3 safety endpoints. In addition, AE summaries (general AEs, serious AEs, drug-related AEs, serious and drug-related AEs, and AEs resulting in discontinuation) by asthma status will also be provided. For pulmonary function test parameters, a cLDA model-based analysis will also be conducted (see Section 3.2.5.1 for more details about the cLDA model).

[Table 4] summarizes the safety tier and level of analysis for the safety endpoints.

Table 4 Analysis Strategy for Safety Parameters

Safety Tier	Safety Endpoint a	p-Value	95% CI for Treatment Comparison	Descriptive Statistics
Tier 1	Proportion of subjects reporting pre-specified local application site reactions (including adverse events related to lip swelling/edema, mouth swelling/edema, palatal swelling/edema, swollen tongue/edema, oropharyngeal swelling/edema, pharyngeal edema/throat tightness, oral pruritus, throat irritation, tongue pruritus, and ear pruritus);  Proportion of subjects reporting anaphylaxis and/or systemic allergic reactions;  Proportion of subjects treated with epinephrine.	X	X	X
Tier 2	Any AE; Any Serious AE; Any Drug-Related AE; Any Serious and Drug-Related AE; Discontinuation due to AE; Specific AEs or SOCs b (incidence $\geq$ 1% of subjects in		X	X
Tier 3	Change from baseline in laboratory test parameters at each post-baseline visit; Change from baseline in vital sign parameters at each post-baseline visit; Change from baseline in pulmonary function test parameters at each post-baseline visit; Summaries by SOC for general AEs, serious AEs, drug-related AEs, serious and drug-related AEs, and AEs resulting in discontinuation; AE summaries by asthma status; Average duration of AEs in minutes on Day 1;  Average duration of AEs in days over Day 2 to Day 14; Average duration of AEs in days over Day 15 to			X

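### Height is scheduled only at Visits 1 and 2, so percent-predicted lung function at Visits 6, 7 and 8 has no current height, and within-arm change would drift upward in growing children if the Visit 2 height is carried forward

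*Protocol*

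**What the plan says.** In the protocol's flow chart (Section 6.0), the row "Body Height and Weight" is marked at Visits 1 and 2 and blank afterwards. Section 7.1.2.2 adds no further time point; it refers back to the chart. The row "Pulmonary Function Tests" is marked at Visits 1, 2, 6, 7 and 8. Footnote k says of vital signs, height and weight: "height, and weight should be performed prior to performing pulmonary function tests".

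Protocol Section 7.1.2.5 lists the parameters: "Pulmonary function tests (PFTs) will include measurements of FEV₁, FEV₁ percent predicted, forced vital capacity (FVC), and FVC percent predicted". Footnote m limits who is tested later: "Following randomization, PFTs are required only for subjects with asthma at the subsequent visits identified in the trial flow chart". A subject without asthma may also be tested if the investigator thinks it warranted, and children aged 7 or under who cannot perform reproducible manoeuvres are exempt.

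The sSAP (Section 3.2.5.2), like protocol Section 8.2.5.2, lists under Tier 3: "Change from baseline in pulmonary function test parameters at each post-baseline visit". Point estimates are reported, and a cLDA model is fitted as well.

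Neither document names a reference equation or says which height or age enters the predicted value after Visit 2. The baseline definitions in protocol Section 8.2.3.4 and sSAP Section 3.2.3.4 cover laboratory tests and vital signs only.

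**The concern.** A predicted FEV1 or FVC rises with height. If a child has grown and the old height is used, the predicted value is too low and percent predicted is too high. Raw FEV1 and FVC in litres also rise as a child grows, so percent predicted is the only listed parameter that can correct for growth. With height frozen at Visit 2 it loses much of that correction.

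The subjects are 5 to 17 years old, and Visit 8 falls about five to seven months after Visit 2. A group whose lung function fell slightly relative to its size could then show no change, or a gain. This would occur in a safety summary of the children with asthma, the group for whom the protocol restricts entry to controlled disease on safety grounds (Section 4.2.1). A height not recorded at the visit cannot be recovered later.

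**Working it through.** The plan gives no figure on this point, so there is none to reproduce. The check compares the schedule rows and then sizes the drift on the condition that the Visit 2 height is reused.

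**Schedule.** Height: Visits 1, 2. Lung function: Visits 1, 2, 6, 7, 8. The three post-randomization test visits have no height. Footnote k can be read in two ways:
- If height must precede every lung function test, the height row contradicts the footnote at Visits 6, 7 and 8.
- If it only sets the order at visits where height is scheduled, no current height is planned for those visits.

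**Time since Visit 2 (from the documents).** Section 2.1 gives about 12 to 20 weeks of pre-seasonal treatment and about 8 weeks in season. The flow chart puts Visit 6 about 2 weeks before the season starts, Visit 7 about 3 weeks after it starts, and Visit 8 about 1 week after it ends. Nominally:
- Visit 6: 12 − 2 = 10 to 20 − 2 = 18 weeks
- Visit 7: 12 + 3 = 15 to 20 + 3 = 23 weeks
- Visit 8: 12 + 8 + 1 = 21 to 20 + 8 + 1 = 29 weeks

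**Assumptions (not in the documents).** Predicted value proportional to height to the power k, with k from 2.0 to 3.0; true percent predicted stable at B = 90; starting height H and growth rate g as in the table.

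**Formula.** Drift in percentage points = B × [((H + g × w/52)/H)^k − 1], where w is weeks since Visit 2.

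Lowest Visit 8 value for a 125 cm child: growth 5 × 21/52 = 2.02 cm; 90 × [(127.02/125)^2 − 1] = 2.9. Highest: growth 7 × 29/52 = 3.90 cm; 90 × [(128.90/125)^3 − 1] = 8.7.

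| Assumed child | Visit 6 | Visit 7 | Visit 8 |
|---|---|---|---|
| 125 cm, 5–7 cm/year | +1.4 to +5.3 | +2.1 to +6.9 | +2.9 to +8.7 |
| 155 cm, 6–10 cm/year (growth spurt) | +1.3 to +6.2 | +2.0 to +7.9 | +2.8 to +10.1 |
| 168 cm, 0–2 cm/year (near-adult) | 0 to +1.1 | 0 to +1.4 | 0 to +1.8 |

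**Central case at Visit 8** (125 cm, 6 cm/year, k = 2.5): +4.4 points at 21 weeks and +6.1 at 29 weeks, that is, overstatement by factors of 1.049 and 1.068. A true fall from 90 to 90/1.049 = 85.8, or to 90/1.068 = 84.2, would still read as 90. The hidden decline is therefore about 4 to 6 points.

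**Between arms.** Assignment is randomized and stratified by age and asthma status, so expected growth, and hence expected drift, is the same in both arms. It cancels on average in the MK-3641 minus placebo difference. Unequal growth among children adds some noise, which is not quantified here.

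**With the fix.** If height is measured at the visit and used, the stale-height drift is zero. No sample size or power figure changes.

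**The case against.** A reader might infer that the reported within-arm changes will be inflated. The documents do not support this as a fact. They never say that the Visit 2 height is reused, and footnote k can be read as already requiring height before each test. On that reading the only defect is a flow chart row that does not match its footnote. This stands, and it makes the drift conditional. It does not remove the point, because a site following the chart as written takes no height at Visits 6, 7 or 8. The allowance in Section 7.1 for unscheduled procedures when clinically necessary does not fill that gap.

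A reader might also infer that all enrolled children are affected. They are not: later testing is required only in subjects with asthma. Drift is close to zero in those who have nearly stopped growing. Section 4.2.1 aims for about 35% aged 5 to 11, which leaves about 65% aged 12 to 17, although that group also includes children in a growth spurt. The documents do not give the age mix within the asthma group.

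The consequence is also limited. The output is Tier 3, and the cLDA in sSAP Appendix A estimates the treatment difference at each time point, where a decline caused by the drug would still show against placebo. Percent predicted has a threshold role only for eligibility at Screening and Randomization, where height is measured; the discontinuation criteria in Section 5.8 cite no FEV1 percentage. All of this stands and limits the weight of the point.

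Finally, the growth rates, heights and exponents are outside assumptions. If the equation also has an age term and current age is entered, part of the drift could be absorbed.

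**Conclusion.** The point holds in conditional form, as a cheap improvement. The mismatch between the height row, footnote k and the lung function schedule is in the documents and does not depend on any assumption. If the Visit 2 height is carried forward, which is what the schedule implies because no later height is planned, within-arm percent predicted would be biased upward in growing children. The drift at Visit 8 would be roughly 3 to 10 percentage points in younger or fast-growing children and about 0 to 2 points in near-adult subjects, with smaller amounts at Visits 6 and 7. These figures rest on the assumed 90% starting value, heights, growth rates and exponents of 2.0 to 3.0.

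At that size a modest within-arm decline could be masked in children with asthma. The documents do not support extending this to a biased treatment comparison: the randomized difference is unbiased on average. The primary and key secondary efficacy analyses do not use lung function and are unaffected.

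**What to change.** Reconcile footnote k with the height row by marking height at Visits 6, 7 and 8 for subjects having lung function tests, including ad hoc tests in subjects without asthma. State in the protocol or sSAP that percent predicted at each visit is computed from that visit's height and age, using one named reference equation throughout. The same text can define the lung function baseline, which is currently missing.

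The cost is one extra height reading at each of these visits, which already include vital signs and spirometry, and a flow chart amendment. If some visits have already passed without a height, the report should say which height was used, and the within-arm changes in percent predicted should be read with that caution.
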